7.5 Pharmacokinetic Endpoints

All PK summaries will be performed as the integrated analysis based on the PKS according to the actual treatment received. The PKS will include all participants in the ATS that received AL002, had at least one

post-dose measurable concentration, and are non-e4/e4. The treatment groups will include AL002 15 mg/kg, AL002 40 mg/kg, AL002 60 mg/kg, AL002 40+60 mg/kg, and LTE titration. There are two titration strategies specified in the protocol (Section 5.1). If there are sufficient number of participants who follow the titration algorithm 2, the PK summary analysis will display both LTE titration Algorithm 1 and Algorithm 2 groups instead of LTE titration groups.

AL002 concentration will be summarized by analysis visit (refer to [Table 7-22](#) to [Table 7-25](#) for analysis visit window definitions) and nominal time point as collected, separately for serum and CSF PK data. Summary statistics will include coefficient of variation (CV) as percent and geometric mean in addition to the descriptive statistics (excluding Q1 and Q3) described in Section 7.1.

AL002 mean (+ SD) concentration-time data will be plotted (linear and semi-log) by elapsed time since the first study drug administration (in weeks, i.e., (time of collection – time of the first study drug administration)/(24×7)) and treatment group, separately for serum and CSF PK. The same plot (linear and semi-log) will be repeated for the first 28 days on treatment period, but by days (i.e., (time of collection – time of the first study drug administration)/24) instead of weeks.

For the summaries and mean plots of AL002 concentrations, concentrations that are below LLOQ (below the limit of quantifications (BLQs)) before the first measurable concentrations on Study Day 1 will be set to zero, and all BLQs after Study Day 1 will be set to missing. The rules specified in Section 7.1.4.1.1 do not apply to PK.

Potential correlations of serum and/or CSF PK data with demographics, safety (including QT changes), efficacy, and PD measures may be explored, as data allow. Additional modeling, including population PK analysis and/or PK/PD analysis to characterize these correlations may be performed. These additional analyses of PK/PD data will be covered in a separate analysis plan and reported separately from the CSR.

The AL002 concentration data will be listed for the ATS..

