### **1.2.2. Clinical Studies**

Study AL002-1 assessed the safety, tolerability, PK, and pharmacodynamics (PD) of IV administration of AL002 administered as a single-dose to healthy volunteers as well as multiple doses to participants with mild to moderate AD. Study AL002-1 was closed to enrollment by Alector on 14 May 2020 given the available data already obtained and limitations on enrollment due to the coronavirus disease 2019 (COVID-19) pandemic.

AL002 was studied in 64 healthy volunteers enrolled in the first portion of the AL002-1 study, which evaluated single-dose IV infusion administration of AL002 with doses ranging from 0.003 to 60 mg/kg. All participants in these single-ascending dose cohorts reached the end of their dose-limiting adverse event (DLAE) assessment windows. Fifty-three participants were exposed to AL002, and 11 participants were on placebo. All participants have completed the study, with the exception of 1 participant (60 mg/kg), who withdrew consent after receiving one dose of AL002. The second portion of AL002-1 evaluated AL002 administered in multiple doses in participants with AD. Due to the closing of enrollment, only 5 of the planned 32 participants with AD were enrolled in the multiple dosing part. Three participants (2 on AL002 and 1 on placebo) were enrolled on a schedule that evaluated AL002 15 mg/kg weekly for 4 doses. Following a protocol amendment, an additional 2 participants (1 on AL002 and 1 on placebo) were enrolled on a schedule that evaluated AL002 60 mg/kg every 4 weeks for 2 doses. In this study, there were no deaths, no DLAEs, no treatment-related serious adverse events (SAEs), and no adverse events of special interest (AESIs). One participant in the pooled placebo group had a Grade 3 injury (attributed to trauma) that was serious and was considered unrelated to study drug. Two participants in the single-ascending dose part experienced adverse events (AEs) considered probably related to AL002 that led to withdrawal of study drug. Overall, AL002 was considered generally safe and well tolerated in this trial.

In the ongoing, randomized, double-blind, placebo-controlled, dose-ranging Phase 2 study, AL002-2, the AL002 is administered for up to 96 weeks via IV infusion every 4 weeks. To

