3. STUDY DESIGN

3.1 Study Design

This is a Phase 2, LTE study of participants with AD. The study will enroll participants who completed the planned treatment period in AL002-2 (Core Study). Study sites are located in North America, Australia, Europe, and Argentina.

Participants who were randomized to active treatment in the Core Study will remain on their previously assigned dose. Participants who were previously on placebo in the Core Study will be assigned to the Titration Cohort (TC), which will initiate with a starting dose of either 2 mg/kg or 6 mg/kg that will be increased over 32 weeks or 24 weeks, respectively, to reach the target dose of 60 mg/kg per the Titration Algorithm (for details of the Titration Algorithm, refer to the Study Protocol).

The planned duration of the LTE study is 56 weeks, and LTE study treatment extends from LTE Day 1 to Week 48. Dosing duration may be extended beyond this time through a protocol amendment, within the context of emerging favorable safety data. AL002 will be administered via IV infusion at the study site on Day 1 (after all necessary baseline assessments have been completed) and will be repeated subsequently once every 4 weeks throughout the treatment period.

The first dose of the AL002-LTE should be within the 4-week window (± 5 days) of the last dose of the Core Study, to maintain continuity of study treatment. Delays of the first AL002-LTE dose beyond that window will constitute protocol deviations.

Dosing for any individual participant may be stopped, paused, or reduced based on emerging safety data and/or the development of ARIA-E or ARIA-H. If a participant discontinues the study prior to the end of their planned treatment period, they will need to return for an Early Termination (ET) Visit and that will mark the end of their participation in the study.

At study entry and throughout the treatment period, safety will be assessed through monitoring of AEs (including AESIs and SAEs), changes in laboratory and vital sign values, incidence of findings from physical, neurological, ECG, MRI, ophthalmological exams, and reports of suicidal ideation or behavior. Serum PK will be assessed for investigation of exposure-response and exposure-safety relationships. Blood samples for assessment of ADA will be taken throughout the study.

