3.2 Participant Grouping

There are two treatment classes for the LTE and Integrated Analyses:

- **Group T-T** includes participants who were exposed to AL002 during the Core Study. They will continue at their Core Study AL002 dosage during the LTE Study if enrolled in the LTE Study. Group T-T is further broken down as AL002 15 mg/kg, 40 mg/kg, and 60 mg/kg treatment groups.

- **Group P-TC** includes participants who were exposed only to placebo during the Core Study. They will be assigned to the TC during the LTE Study if enrolled in the LTE Study. Group P-TC might be separated into placebo and TC treatment groups depending on the summaries/analyses.

For Group P-TC, the data collected when the participants were receiving placebo in the Core Study might be summarized and/or analyzed separately from the data collected once the participants received the first study drug administration in the LTE Study. The data collected when the participants were receiving placebo in the Core Study up to the day before the participants received the first study drug administration in the LTE Study (separately from the data collected in the LTE Study) is referred to as **the Placebo Data** throughout the SAP. And it includes the data from the placebo participants who did not enroll in the LTE Study. The data collected on or after the day when the participants received the first study drug administration in the LTE Study is referred to as **the TC Data** throughout the SAP.

The first dose date of AL002 refers to the earliest date of any amount of AL002 administered across the Core Study and the LTE Study. **The last dose date of AL002** refers to the latest date of any amount of AL002 administered across the Core Study and the LTE Study. **The first dose date of any study drug** refers to the earliest date of any study drug administered, including placebo, across the Core Study and the LTE Study.

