7.1.1 Study Day and Visit Window Definitions

7.1.1.1 Study Day

The first date on which participant receives study drug (or study treatment – AL002 or placebo) per the records with non-missing dates and non-missing volume administered in the dataset corresponding to the Exposure – IV electronic CRF in the Core Study will be designated as **Core Study Day 1**. Similarly, the first day of AL002 treatment in the LTE Study will be designated as **LTE Study Day 1**. Study days for other visits will be calculated as follow:

- Before Core Study Day 1: Core Study Day = date of assessment – date of Core Study Day 1.
- On or after Core Study Day 1: Core Study Day = date of assessment – date of Core Study Day 1 + 1.
- Before LTE Day 1: LTE Study Day = date of assessment – date of LTE Study Day 1.
- On or after LTE Day 1: LTE Study Day = date of assessment – date of LTE Study Day 1 + 1.

Core Study Days continue when participants enroll in the LTE Study and are applicable to both Group T-T and Group P-TC. LTE Study Days are only applicable to Group P-TC.

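### SAP 7.5 times the PK mean plots from the first study drug dose, which for the Titration Cohort is, as written, a Core placebo infusion

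*SAP*

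**What the plan says.** SAP 7.5 plots mean serum and CSF concentrations by treatment group "by elapsed time since the first study drug administration". The same origin stands in the formula for elapsed weeks and in the formula for elapsed days, which serves a second plot limited to the first 28 days. LTE titration is one of the listed groups.

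The SAP treats placebo as study drug. Section 7.1.1.1 starts the Core clock on "The first date on which participant receives study drug (or study treatment – AL002 or placebo". Section 3.2 keeps two dates apart. One counts only AL002 infusions, in whichever study they were given. The other is wider and "refers to the earliest date of any study drug administered, including placebo, across the Core Study and the LTE Study". Section 7.5 does not use the AL002 term. Group P-TC, which supplies the Titration Cohort, "includes participants who were exposed only to placebo during the Core Study".

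For the summaries and mean plots, 7.5 sets BLQ values to zero if they precede the first measurable concentration on Study Day 1. Beyond that, "all BLQs after Study Day 1 will be set to missing". It does not say whether Study Day 1 means the Core or the LTE day, although 7.1.1.1 defines both.

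**The concern.** The titration regimen is the new dosing schedule in this study, and PK is a secondary objective. A reader will expect the Titration Cohort curve to show concentration against time on AL002. A programmer who follows the formulas in 7.5 would instead measure time from a placebo infusion given up to about two years earlier. The curve would then sit far to the right of the other dose groups, and its early-exposure plot would show nothing about AL002.

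The unqualified Study Day 1 adds a smaller problem of the same kind. If it means the Core day, a Titration Cohort pre-dose BLQ on LTE Day 1 becomes missing instead of zero, although the participant has not yet received AL002.

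Separately, a rule that drops only the lowest values from a mean, and does not report how many were dropped, can make low exposures look higher than they were.

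**Working it through.** **Time origin**

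Inputs:
- In the parent study, AL002 "is administered for up to 96 weeks via IV infusion every 4 weeks" (Protocol 1.2.2).
- The first LTE dose is due 4 weeks ±5 days from the end "of the last dose of the Core Study, to maintain continuity of study treatment" (SAP 3.1).
- Target days for serum PK are 729 for Core Week 104 (SAP Table 7-22) and 29 for LTE Week 4 (Table 7-23).
- Titration lasts 32 weeks from 2 mg/kg or 24 weeks from 6 mg/kg (SAP 3.1).

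1. *Offset after full Core treatment.* 729 − 29 = 700 days, and 700/7 = 100 weeks. This agrees with 96 + 4 = 100. With ±5 days, the range is 695/7 = 99.3 to 705/7 = 100.7 weeks.
2. *Plotted position.* Elapsed week = LTE week + 100. LTE Day 1 plots at week 100, LTE Week 24 at 124 and LTE Week 48 at 148. Timed from the first AL002 dose, they would plot at 0, 24 and 48.
3. *28-day plot.* All AL002 exposure in this group begins at about day 700, so none falls in the first 28 days. The plot holds placebo-period samples if these are included and is empty if they are not.
4. *Shorter Core treatment.* The plan allows for LTE entry before Core Week 96. Placebo windows in Table 7-22 are cut at LTE Day 1 from Week 48 onward, and SAP 7.6.2 draws on LTE data for AL002 groups within the first 96 weeks. The spread is not stated. Suppose, as an assumption, that one participant had 48 weeks of Core treatment. The offset is then 48 + 4 = 52 weeks. At elapsed week 100 this participant is at LTE Week 100 − 52 = 48, past the end of either titration, while a full-Core participant is at the first dose. The plot would average the two.
5. *By-visit tables.* Table 7-22 closes the placebo column at LTE Day 1. Later Titration Cohort samples go to Table 7-23 (serum) or Table 7-25 (CSF), both on LTE Study Day. These summaries are placed correctly.

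**BLQ values**

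The documents give no quantification limit, variability or expected BLQ fraction, so the following is illustrative. Assume lognormal concentrations with coefficient of variation CV and BLQ fraction q. Let s = √ln(1 + CV²) and let z be the standard normal q-quantile.

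- Mean of measurable values over true mean: Φ(s − z)/(1 − q).
- The same ratio for geometric means: exp[s·φ(z)/(1 − q)].

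Example with CV 80% and q = 10%: s = 0.703, z = −1.282, Φ(1.985) = 0.976, and 0.976/0.9 = 1.085, an inflation of about 8.5%.

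| BLQ fraction | Mean inflated by (CV 40% to 120%) | Geometric mean inflated by |
|---|---|---|
| 0% | 0 | 0 |
| 5% | 3% to 5% | 4% to 11% |
| 10% | 6% to 10% | 8% to 20% |
| 25% | 14% to 26% | 18% to 49% |
| 50% | 30% to 66% | 36% to 112% |

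**The case against.** The placebo origin may not be intended. The plotted group is named for the LTE titration, the short plot is described as on treatment, no placebo group is listed in 7.5, and Section 3.2 elsewhere ties the first administration expressly to the LTE Study. An empty or far-shifted figure would probably be noticed. This stands as evidence of intent. It does not repair the text, because 7.5 omits the qualifier and both formulas carry the wider term.

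The 28-day plot would be thin even with the right origin. Table 7-23 has no serum visit between LTE baseline and LTE Week 4, and Protocol Table 9, footnote i, makes samples at dosing visits pre-dose. That also stands.

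A reader might infer three stronger things that the documents do not support:
- *That all Titration Cohort PK is misplaced in time.* The tables use LTE Study Day; only the mean plots are affected.
- *That the profile is biased upward.* This needs BLQ values after Study Day 1, and nothing shows how many to expect. Early troughs after 2 or 6 mg/kg are the plausible place. The scheduled LTE CSF sample at Week 48 and the sample 8 weeks after the last dose come after planned titration has ended. The rule also covers every AL002 group, and the concentrations are still listed.
- *That the exposure analyses of amyloid-related imaging abnormalities (ARIA) are distorted.* SAP 7.5 sends additional PK/PD modelling to a separate plan and limits the BLQ rule to summaries and mean plots.

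**Conclusion.** The timing point holds as a defect of wording in 7.5. Applied literally, it displaces the Titration Cohort mean curves by about 100 weeks after full Core treatment, and by less where Core treatment was shorter, in which case titration steps can also be mixed. It leaves no AL002 profile in that group's 28-day plot. The conclusion rests on the SAP's own use of study drug to include placebo. It is confined to descriptive plots for a secondary endpoint; no hypothesis test, error rate or tabulated by-visit summary depends on it. It is still worth correcting, because a stated rule yields a wrong figure.

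The BLQ point is secondary. The direction is certain wherever BLQ values occur, since only the lowest values are removed. The PK Set also requires one measurable post-dose concentration, so a participant with none is left out altogether. The size is unknown and may be zero.

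**What to change.** In SAP 7.5, including both formulas, replace the first study drug administration by the first AL002 administration, and add that this is LTE Study Day 1 for the titration groups. State that Study Day 1 in the BLQ rule means LTE Study Day 1 for those groups.

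Report the number and percentage of BLQ values per visit and group. Beside the planned rule, add a sensitivity summary with BLQ values imputed, for example at half the quantification limit. That imputation has a bias of its own. In the same lognormal model, the mean is 0.5% (10% BLQ) to 1.9% (30% BLQ) too low at CV 100%, and 1.2% to 4.4% too low at CV 60%. Statisticians differ on the best substitute, so it should accompany the planned rule and not replace it.

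The cost is a few words in the SAP and one extra table. No data collection changes, and keeping the planned BLQ rule as the main summary avoids introducing a new difference from the Core Study's PK reporting.

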7.6 Efficacy Analyses

All efficacy endpoints will be summarized with the Integrated Analysis for the FAS. Analysis sets are defined in Section [Error! Reference source not found.](#)

The main estimand as described in Section 0 will be used for all efficacy analyses. The supportive estimand may be used as additional analysis for some efficacy endpoints.

Analysis visit windows for efficacy data are defined in Section 7.1.1.2.2. Baseline is defined in Section 7.1.2.

7.6.1 Descriptive Summaries of Efficacy Endpoints

The integrated descriptive summary of an efficacy endpoint including the Placebo Data will summarize all the data collected in the Core Study and in the LTE Study with descriptive statistics, by individual placebo/TC, AL002 15 mg/kg, 40 mg/kg, and 60 mg/kg, and the TC treatment groups, and AL002 40 and 60 mg/kg combined group.

The CFB and PCFB will be based on the Core baseline for placebo/TC, AL002 15 mg/kg, 40 mg/kg, and 60 mg/kg, and AL002 40 and 60 mg/kg combined treatment groups. The CFB and PCFB for the TC will be based on the LTE baseline. And all analysis visits from the Core and LTE Studies will be included.

Longitudinal trend (line-plot) figures (group mean [unadjusted] of change from Core baseline \pm SEM (standard error of the mean) over time at each analysis visit) over the Core + LTE periods for placebo/TC, AL002 15 mg/kg, 40 mg/kg, and 60 mg/kg treatment groups will be created.

7.6.2 Analyses of Efficacy Endpoints

For Integrated Analysis, the analyses as described in the Core Study SAP will be repeated based on the integrated data up to Week 96 since the initiation of study treatment from both the Core Study and the LTE study for the AL002 treatment groups and the data from the Core Study and the screening visit of LTE study for the placebo treatment group. This includes the fitting of MMRM and pMMRM models, to obtain estimates of least square mean difference in CFB and percent slowing of decline (from MMRM) and proportional treatment effect (from pMMRM).

A pMMRM approach (G. Wang et al., 2022) will be used as the primary analysis of all efficacy endpoints. Conceptually, the pMMRM is similar to the Cox proportional hazards model, as it models the treatment effect as a single proportional difference at each post-baseline visit. It uses time as a categorical variable like an MMRM and thus avoids the linearity assumption. On the other hand, pMMRM takes on the assumption of a proportional treatment effect of a linear mixed-effect (LME) model and thus uses assessments more efficiently than an MMRM model.

A restricted maximum likelihood based MMRM will be used as a supportive analysis to assess the primary endpoint. The SAS® MIXED procedure will be used to fit an MMRM with CFB in CDR-SB at each scheduled post-baseline visit (Week 24, 48, 72, and 96) as the dependent variables and the fixed effects will include following items:

- Treatment group,
- Visit (categorical, as week),
- Visit-by-treatment interaction,
- Core Baseline CDR-SB score (covariate),
- APOE e4 status (covariate, e4 carrier vs non-e4 carrier).

An unstructured covariance matrix will be used to model within-participant variance-covariance errors. If the unstructured covariance structure matrix results in a lack of convergence, the following tests will be used in sequence:

- Heterogeneous Toeplitz (TOEPH) covariance structure,
- Heterogeneous first-order autoregressive (ARH(1)) covariance structure,
- Heterogeneous compound symmetry (CSH) covariance structure,
- Toeplitz (TOEP) covariance structure,
- First-order autoregressive (AR(1)) covariance structure,
- Compound symmetry (CS) covariance structure.

In the case that a structured variance-covariance matrix is used to enable the model to converge, the "sandwich" estimator of the variance-covariance matrix will be employed by using the "empirical" option in the SAS PROC MIXED procedure.

The MMRM and pMMRM modeling analyses will not be performed at the first IA at the time of unblinding of the Core Study due to limited data from the LTE study at this IA, but will be performed in all analyses after the first IA.

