6.4.1.1 Main Estimand for Efficacy

- Treatment condition: Group T-T (AL002 15 mg/kg, 40 mg/kg or 60 mg/kg IV Q4W) continues their Core study treatment in the LTE Study; whereas Group P-TC treated with Placebo in the Core study will be titrated up to 60 mg/kg of AL002 in the LTE study.
- Target population: adult participants with AD excluding APOE e4/e4 participants.
- Efficacy endpoint: CFB in CDR-SB.
- Accounting for intercurrent events: a composite strategy will be used to handle intercurrent events as below:
 - Hypothetical strategy for handling premature study drug discontinuation for any reason (data will be considered missing after a participant prematurely discontinued study drug plus 37 days).
 - Treatment policy strategy for handling all other intercurrent events.
- Population-level summary: the percent reduction relative to placebo decline (the proportional treatment effect), comparing each dose level to placebo.

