7. STATISTICAL ANALYSIS

7.1 General Data Handling Rules and Definitions

“AL002 40 and 60 mg/kg combined group” refers to the group pooling AL002 40 mg/kg and 60 mg/kg treatment groups. And “AL002 total” refers to the group pooling AL002 15 mg/kg, 40 mg/kg, and 60 mg/kg, and the TC treatment groups.

Assessments collected in the Core and LTE Study that will be provided in by-participant data listings are specified in each respective section. If any dosed participant is found to not have valid documented informed consent, that participant’s data will be excluded from the report, except as necessary to document the error. By-participant data listings will be presented for data collected in the Core and LTE Study for all participants and sorted by treatment group, participant identification (ID) number, visit date, and time (if applicable), unless otherwise specified. Data collected on log forms, such as AEs, will be presented in chronological order for each participant. Age at time of informed consent in the LTE Study, sex at birth, race, and ethnicity will be included in the listings.

Analyses (including analysis sets that analyses will be conducted on) to be performed for each interim analysis (IA) are specified in Section 8.

All analyses will be conducted using SAS® version 9.4 or later.

Except where specified, all continuous variables will be summarized with descriptive statistics (the number of non-missing values, mean, standard deviation (SD), median, 25% quartile (Q1), 75% quartile (Q3), minimum (min) and maximum (max)) and all categorical variables will be summarized with frequency counts and percentages, by treatment group.

Missing data will be assumed as missing at random (MAR) for all analyses and will not be imputed, unless otherwise specified.

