7.7.3 Pharmacodynamic (PD) Assessment of Biomarker Endpoints

For Integrated Analysis, similar analyses listed in section 7.6.2 for efficacy endpoints will be provided for biomarker endpoints. Specifically, for CSF and plasma biomarkers, volumetric MRI, amyloid PET and Tau PET parameters [Table 7-39], the analyses will be based on the integrated data up to Week 96 since the initiation of study treatment from both the Core Study and the LTE study for the treatment groups and the data from the Core Study and the LTE screening data for the placebo treatment group. Specifically, the MMRM will be fit with CFB in biomarkers up to Week 96 as the dependent variable, and treatment group, categorical visit, visit-by-treatment interaction, baseline (from the Core Study) biomarker, and APOE e4 status of carrier vs. non-carrier as fixed effects.

Input for the models will be non-missing data at all analysis visits up to and including Week 96, as specified in Tables Table 7-12, Table 7-28, Table 7-30, Table 7-32, and Table 7-36. Treatment comparisons will be reported for specified visits as indicated below:

- Plasma biomarkers:
 - AD-pathology (A β 42/40, pTau217): week 12, 24, 48, 72 and 96
 - AD-pathology (MTBR Tau-243 [if available]): week 12, 24, 48, 72 and 96
 - AD-pathology (pTau181 [if available]): week 16, 36, 60 and 84
 - Target engagement (IL1RA): week 1, 2, 4, 6, 8, 12, 24, 36, 48, 72 and 96
 - Neurodegeneration (NfL, GfAP): week 12, 24, 48, 72 and 96
- CSF biomarkers: week 6, 48, 72 and 96
- Amyloid PET parameters: week 48 and 96
- Tau PET parameters: week 48, 72 and 96
- Volumetric MRI parameters: week 48, 72 and 96

Model results, including treatment comparisons will also be obtained as “overall” for the average over all analysis visits in the model.

For Tau PET parameters [Table 7-39], a pMMRM model will be additionally conducted. The integrated PD analyses via MMRM and pMMRM will be based on the subset with redefined core baseline.

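### The MMRMs hold the baseline slope constant across all visits to Week 96; a baseline-by-visit term is a cheap protection in case that slope changes

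*SAP*

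**What the plan says.** SAP 7.6.2 fits an MMRM to change in CDR-SB "at each scheduled post-baseline visit (Week 24, 48, 72, and 96) as the dependent variables". Its fixed effects are treatment, categorical visit, their interaction, Core baseline CDR-SB and APOE e4 carrier status. The baseline entry reads "Core Baseline CDR-SB score (covariate") and the only interaction listed is "Visit-by-treatment interaction". On covariance: "An unstructured covariance matrix will be used to model within-participant variance-covariance errors".

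For efficacy this model is secondary: "A restricted maximum likelihood based MMRM will be used as a supportive analysis to assess the primary endpoint". The pMMRM is primary for all efficacy endpoints. Its covariates are not listed; 7.6.2 refers to the Core Study SAP, which is not among the documents. The MMRM supplies the least-squares mean differences and the percent slowing.

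SAP 7.7.3 specifies the biomarker MMRM with "treatment group, categorical visit, visit-by-treatment interaction, baseline (from the Core Study) biomarker, and APOE e4 status of carrier vs. non-carrier as fixed effects". A pMMRM is added for Tau PET only. These models take data from every analysis visit up to Week 96: 14 plasma visits (Table 7-28) and nine MRI visits, five of them by Week 12 (Table 7-12).

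Under the main estimand (6.4.1.1), "data will be considered missing after a participant prematurely discontinued study drug plus 37 days". SAP 7.1 adds: "Missing data will be assumed as missing at random (MAR) for all analyses and will not be imputed".

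**The concern.** A single baseline coefficient says that one extra point at baseline predicts the same additional change at Week 24 as at Week 96, or at Week 1 as at Week 96 for plasma markers. If the relation in fact strengthens with time, the common slope is pulled toward the early, less variable visits. Part of the predictable variation at Week 96 then stays in the residual.

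The second consequence concerns missing data. With scores set to missing after discontinuation and no imputation, the likelihood predicts late scores from baseline and earlier visits. When dropout depends on baseline, that prediction is right only if the mean model is right given baseline. If the arms also differ in how dropout depends on baseline, the error does not cancel in the treatment difference. At stake is the Week 96 estimate in the supportive efficacy model and in the exploratory biomarker models.

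**Working it through.** **The plan's own figure.** SAP 3.5 gives 220 eligible Core participants and 80-90% rollover: 220 × 0.80 = 176 and 220 × 0.90 = 198, as stated. This has no bearing on the model terms. It serves only as a basis for an illustrative arm size, 220/4 = 55. The documents give no arm sizes for the FAS, and no slopes, SDs or dropout rates for these models. All inputs below are assumptions.

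**Why bias needs several conditions together.** Let the true slope at visit t be b_t, the fitted common slope b*, and d_t = b_t − b*. For someone who leaves early, the model predicts Week 96 from baseline and earlier residuals. The part it misses, per baseline point, is e = d_96 − γ′d_early, where γ holds the regression coefficients of the Week 96 residual on the earlier ones. Approximately,

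bias of an arm mean = p × e × (mean baseline of completers − mean baseline of leavers),

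where p is the share missing at Week 96. If the slope is constant, e = 0. If dropout is random, the bracket is 0. If dropout depends on baseline equally in both arms, the product cancels in the difference. With rising slopes and high-baseline participants leaving the AL002 arm, the bias is negative (an apparent benefit, since higher CDR-SB is worse). The opposite dropout pattern reverses the sign.

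**Simulation inputs.** Two arms, four visits, no true effect, baseline SD 1.5, unstructured covariance.

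- Set A: residual SD 1.2/1.8/2.3/2.8, correlation 0.8^lag, 60 per arm, Week 96 decline 2.5. Slopes rise 0.05 to 0.32 or 0.10 to 0.50. In the AL002 arm only, dropout log-odds rise 0.25-0.5 per baseline point; 70-73% are observed at Week 96.
- Set B: residual SD 1.0/1.5/2.0/2.5, 55 per arm, Week 96 decline 2.6. Control loss is 10% per interval (1 − 0.9³ = 27%). AL002 dropout log-odds rise 0.8 per point, a strong dependence, with 28% lost.

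**Variance of the Week 96 difference, main effect only ÷ with baseline-by-visit**

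| Slopes | Complete data | With dropout |
|---|---|---|
| A: 0.05 to 0.32 | 1.013 | not run |
| A: 0.10 to 0.50 | 1.067 | not run |
| B: constant 0.2 | 1.00 | 0.96-0.97 |
| B: 0.05 to 0.30 | 1.02 | 1.00-1.01 |
| B: 0.1 to 0.6 | 1.10 | 1.06-1.07 |

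The rising-slope rows of set B use 2,500 replicates. Runs of 1,500 with dropout gave 0.98 and 1.03-1.04 for those rows, so differences of about 3 points are within simulation noise.

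**Bias of the Week 96 difference, baseline-dependent dropout in the AL002 arm only (large-sample fits)**

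| Slopes | Main effect only | With baseline-by-visit |
|---|---|---|
| A, four scenarios | −0.030, −0.047, −0.057, −0.107 | 0.003, 0.000, 0.011, −0.009 |
| B: constant 0.2 | 0.009 | 0.010 |
| B: 0.05 to 0.30 | −0.080 | 0.010 |
| B: 0.1 to 0.6 | −0.164 | 0.010 |

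A separate run of set A gave −0.02 to −0.10. Monte Carlo SE in set B is about √(2 × 2.5²/200,000) = 0.008. The 55-per-arm runs gave −0.089 and −0.174 for the two rising-slope rows, the same within simulation error (0.565/√2,500 = 0.011). Random dropout, or equal dependence in both arms, gave 0.004 to 0.010 under either model, which is simulation error.

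**Scale.** 0.030/2.5 = 1.2% and 0.107/2.5 = 4.3% of decline in set A; 0.080/2.6 = 3.1% and 0.164/2.6 = 6.3% in set B. In set A the complete-data SE is about √(2 × 2.8²/60) = 0.51, so the bias is about 0.06 to 0.2 SE. Type I error in the strongest CDR-SB-like case was 0.062, against 0.053 with the interaction.

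**A constructed biomarker-like case** (slopes 0 to 0.8, residual SD 0.8/1.1/1.4/1.7): variance ratio 1.53 with complete data and 1.39-1.45 with dropout, bias −0.25, type I error 0.096 against 0.057. It shows what is possible when baseline strongly predicts late change; it represents no particular marker.

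**The case against.** Most of the opposing case stands.

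- **Reach.** The efficacy MMRM is supportive and the biomarker models are exploratory. A reader might infer that the primary efficacy result is affected. The documents do not support that, since the pMMRM covariates are not given.
- **Mechanism.** A reader might infer that ARIA stopping rules make the bias expected, because they fall mainly on AL002-treated participants. Protocol Table 8 stops treatment on radiographic severity, symptoms, seriousness and recurrence, not on CDR-SB or a baseline biomarker. The risk factors named in Protocol 1.4 are APOE e4 homozygosity, dose (from anti-amyloid trials) and early treatment. The FAS excludes e4/e4 participants, and carrier status is already a covariate. Arm-specific dropout is plausible; arm-specific dependence on the baseline score is an assumption.
- **Precision.** An unconditional loss of precision is also not supported. With moderately rising slopes and dropout the gain from the extra term is close to nil. With a constant slope the term costs 0-4% of variance.
- **Comparability.** The integrated analysis is meant to repeat the Core analyses, and the plasma models already carry 14 × 15/2 = 105 covariance parameters.

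What remains is that both MMRMs fix the slope, that MAR-based estimation relies on the mean model, and that nothing in the documents says the slope is constant over 96 weeks.

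**Conclusion.** The point holds as a minor, conditional refinement. Loss of precision requires a slope that changes over visits. Bias requires that and also dropout related to baseline differently by arm; the documents establish neither condition. Under the assumed inputs the CDR-SB consequences are small against the sampling error. Biomarkers strongly predicted by baseline could be affected more, but no figure in the documents allows that to be sized. The bias does not shrink with sample size, yet at this study's size it is a fraction of one SE for CDR-SB.

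**What to change.** Add baseline-by-visit to the fixed effects of the MMRMs in SAP 7.6.2 and 7.7.3. Report the main-effect-only form alongside, for comparability with the Core report. No change to the pMMRM is proposed, since its specification is not available here.

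The cost is one term of difference from the Core model (taking the 7.6.2 list to reproduce it): 4 − 1 = 3 extra parameters for CDR-SB and 14 − 1 = 13 for a plasma marker measured at all 14 visits. If the slope is in fact constant, at most a few percent of variance is lost. The SAP does not fit these models at the first interim analysis, so the plan leaves room to specify the term before they are first fitted.
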